#### **8.4.8 Range of movement**

The passive and active range of movement (RoM) of the joints of the reference digit are measured at baseline and 3, 6, 12 and 24 months post treatment. RoM of joints on the reference digit other than the reference joint will be summarised descriptively and graphically. Active and passive RoM of the reference joint will be analysed using a similar covariance pattern models as used for the primary analysis models, with baseline RoM (active or passive as relevant) and reference digit included in the fixed effect specification and baseline PEM score removed. This model will include all participants with at least one post-treatment measurement of the relevant outcome (active or passive RoM). The estimated between group difference in RoM at each post-treatment follow up will be reported together with two-sided 95% CIs. If baseline range of movement is missing, then it will be imputed using predicted values via regression of the observed measurements on observed baseline MHQ scores and reference joint (MCP or PIP). If MHQ score is also missing, then missing baseline RoM will be imputed with the reference joint strata specific means.

Due to the Coronavirus pandemic, a substantial proportion of participants were followed up remotely at 3, 6, 12 and 24 months post-treatment, and did not have goniometric measurements taken. Missingness due to remote follow up, as well as attrition, mean a substantial proportion of the post-treatment goniometric measurement data will be missing. The proportion of missing data at each time point will be summarised by randomised group, as will the available reasons this missing data. The principal analyses of RoM outlined above (based on the available goniometric measurements) will be repeated

using two alternative analysis sets. The first analysis set will supplement the available goniometric measurements with measurements obtained using photographs taken by clinical investigators. If photographs taken by the clinical investigators are not available, then measurements obtained using photographs taken by the participant will be used (note this would include photographs submitted by participants in the photography sub-study, as well as photographs submitted by non-sub-study participants who could not attend clinic visits due to the pandemic). The second analysis will use the multiply imputed dataset(s) generated as part of the analyses specified in Section 8.3.1. Both analysis sets will be analysed using the same model used to analyse the available goniometric measurements, with the results being reported analogously.

#### **8.4.9 Active Extension**

The active extension of the joints of the reference digit is measured at baseline and 3, 6, 12 and 24 months post treatment. The active extension of joints on the reference digit other than the reference joint will be summarised descriptively and graphically. Active extension of the reference joint following treatment will be analysed using a similar covariance pattern model as used for the primary analysis, with baseline active extension and reference digit added to the fixed effect specification and baseline PEM score removed. This model will include all participants with at least one post-treatment measurement of active extension. The estimated between group difference in active extension at each post-treatment follow up will be reported together with two-sided 95% CIs. If baseline active extension is missing, then it will be imputed using predicted values via regression of the observed measurements on observed baseline MHQ scores and reference joint (MCP or PIP). If MHQ score is also missing, then missing baseline active extension will be imputed with the reference joint strata specific means.

Due to the Coronavirus pandemic, a substantial proportion of participants were followed up remotely at 3, 6, 12 and 24 months post-treatment, and did not have goniometric measurements taken. Missingness due to remote follow up, as well as attrition, mean a substantial proportion of the post-treatment goniometric measurement data will be missing. The proportion of missing data at each time point will be summarised by randomised group, as will the available reasons this missing data. The principal analyses of active extension outlined above (based on the available goniometric measurements) will be repeated using two alternative analysis sets. The first analysis set will supplement the available goniometric measurements with measurements obtained using photographs taken by clinical investigators. If photographs taken by the clinical investigators are not available, then measurements obtained using photographs taken by the participant will be used (note this would include photographs submitted by participants in the photography sub-study, as well as photographs submitted by non-sub-study participants who could not attend clinic visits due to the pandemic). The second analysis will use the multiply imputed dataset(s) generated as part of the analyses specified in Section 8.3.1. Both analysis sets will be analysed using the same model used to analyse the available goniometric measurements, with the results being reported analogously.

#### **8.4.10 Stiffness**

The maximal flexion of the joints of the reference digit is measured at baseline and 3, 6, 12 and 24 months post treatment. The flexion measurements of joints on the reference digit other than the

reference joint will be summarised descriptively and graphically. Flexion of the reference joint following treatment will be analysed using a similar covariance pattern model as used for the primary analysis, with baseline flexion measurements and reference digit added to the fixed effect specification and baseline PEM score removed. This model will include all participants with at least one post-treatment measurement of flexion. The estimated between group difference in flexion at each post-treatment follow up will be reported together with two-sided 95% CIs. If baseline flexion is missing, then it will be imputed using predicted values via regression of the observed measurements on observed baseline MHQ scores and reference joint (MCP or PIP). If MHQ score is also missing, then missing baseline flexion will be imputed with the reference joint strata specific means.

Due to the Coronavirus pandemic, a substantial proportion of participants were followed up remotely at 3, 6, 12 and 24 months post-treatment, and did not have goniometric measurements taken. Missingness due to remote follow up, as well as attrition, mean a substantial proportion of the post-treatment goniometric measurement data will be missing. The proportion of missing data at each time point will be summarised by randomised group, as will the available reasons this missing data. The principal analyses of flexion outlined above (based on the available goniometric measurements) will be repeated using two alternative analysis sets. The first analysis set will supplement the available goniometric measurements with measurements obtained using photographs taken by clinical investigators. If photographs taken by the clinical investigators are not available, then measurements obtained using photographs taken by the participant will be used (note this would include photographs submitted by participants in the photography sub-study, as well as photographs submitted by non-sub-study participants who could not attend clinic visits due to the pandemic). The second analysis will use the multiply imputed dataset(s) generated as part of the analyses specified in Section 8.3.1. Both analysis sets will be analysed using the same model used to analyse the available goniometric measurements, with the results being reported analogously.

#### 8.4.11 Complications

Data pertaining to complications and adverse events related to treatment are collected, in both the investigator completed follow up CRFs and as part of the adverse event reporting. These will be graded according to their severity using an eight level ordinal classification from no complications up to death (Table 4). Grades will be allocated based on the following domains; symptoms, intervention, recovery duration and residual disability. Allocation of a given complication to a particular grade will initially be performed by two observers working independently of one another. A meeting between the two observers will be used to resolve any conflicts in the initial ranking/classification assigned. The justifications for the assignment of a given complication to a particular level will be recorded and will be available for review.

**Table 4:** Ordinal classification used to rank treatment complications;

Level	Definition
None (0)	No complications identified
Technical – not complication (1)	Events related to treatment, but not technically complications (e.g. soft or broken cast, over tight splint)

Very minor (2)	Events related to treatment, but possible to immediately remedy (e.g. removal of retained stich, cast soreness (without pressure sores))
Mild (3)	Events related to treatment, but minor based on symptoms and impact and also reversible
Moderate (4)	Events related to treatment that require treatment/action (and/or have ongoing consequences), but do not require hospitalisation or re-operation (e.g. additional therapy and nurse follow up for stiffness, resolving infection)
Severe (5)	Events related to treatment that require treatment/action (and/or have ongoing consequences), and require hospitalisation or re-operation and may have lasting consequences
Devastating (6)	Events related to treatment that require treatment/action (and/or have significant ongoing consequences), and require hospitalisation or re-operation and have significant lasting consequences (e.g. significant and un-resolving chronic regional pain syndrome)
Death (7)	Death (unexpected in DISC and only allocated as a complication if it is directly attributable to the treatment or intervention (e.g. anaphylactic reaction to administered drug leading to death))

The number and proportion of participants experiencing a complication assigned each level of severity in Table 4 will be reported by randomised group (potentially multiple complications per participant). For further analyses, the highest ranked (i.e. worst) complication experienced will be used.

The highest ranked complication experienced will be cross-tabulated with randomised group. Groups will be compared using a mixed effect proportional odds model (i.e. an ordinal regression model with logit link where the effect of each predictor is constrained to be the same for all levels of the outcome) with fixed effects for allocation (Collagenase or Surgery), reference joint type (MCP or PIP), and reference joint extension deficit at baseline, and a random intercept for study recruitment site. If greater than 10% of cases with non-missing complications data are missing an extension deficit measurement at baseline, then this term will be excluded from the model. If less than or equal to 10% of cases with non-missing complications data are missing an extension deficit measurement at baseline, then these missing baseline measurements will be imputed using the mean of the observed measurements conditional on reference joint type (MCP or PIP), reference digit type (Little vs Ring vs Middle/Index/Thumb) and baseline PEM score. If a participant is also missing a baseline PEM score, then the missing baseline extension deficit measurement will be imputed with the mean of the observed data conditional on reference joint type and reference digit type only. The estimated odds ratio for allocation will be reported, together with a two-sided 95% CI. The fitted model will be used to estimate  $\Pr(Y \geq j | \text{Intervention}, X) - \Pr(Y \geq j | \text{Control}, X)$ , (and two-sided 95% CIs based on standard errors obtained via the delta method) for each level  $j = 1, \dots, 7$ , where  $X$  denotes representative values of the covariates (both levels of reference joint, mean of the observed baseline PEM scores and two levels of reference digit (ring and little)). This analysis will be repeated for a reduced set of complications that excludes skin tears that occur during joint manipulation, as these events are in many cases an expected part of the procedure rather than a treatment complication. The results for this analysis excluding skin tears will be reported in a similar manner to the reporting of the analysis including skin tears.

A partial proportional odds model will also be fitted relaxing the proportional odds assumption for the effect of allocation (but retaining it for the effects of the other covariates). The random intercept for centre will be dropped and cluster robust standard error will be used instead (currently no software implementations of mixed effect partial proportional odds models). The estimated odds ratios for allocation for each outcome level will be reported together with 95% CIs.

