Passive RoM	
3 Months	
6 Months	
12 Months	
24 Months	

**Table xx:** Estimated differences in RoM at each post-treatment time point (Goniometer and photographic measurements)

	Estimated difference (95% CI)
Active RoM	
3 Months	
6 Months	
12 Months	
24 Months	
Passive RoM	
3 Months	
6 Months	
12 Months	
24 Months	

**Table xx:** Estimated differences in RoM at each post-treatment time point (multiply imputed data)

	Estimated difference (95% CI)
Active RoM	
3 Months	
6 Months	
12 Months	
24 Months	
Passive RoM	
3 Months	
6 Months	
12 Months	
24 Months	

**Table xx:** Treatment complications by randomised group (worst single treatment complication experienced)

Level	Collagenase (N = )	Surgery (N = )	Total (N = )
None (0)			
Technical – not complication (1)			
Very minor (2)			
Mild (3)			
Moderate (4)			
Severe (5)			
Devastating (6)			
Death (7)			

**Table xx:** Estimated absolute differences in proportions experiencing complication of level  $j$  or higher, for  $j = 1, \dots, 7$  from fitted proportional odds model

Covariate values (X)	Level	Absolute difference (95% CI) ( $\Pr(Y \geq j   \text{collagenase, X}) - \Pr(Y \geq j   \text{surgery, X})$ )
Joint = MCP Digit = Ring PEM = mean	$j = 1$ (Technical)	
Joint = MCP Digit = Little PEM = mean	$j = 1$ (Technical)	
Joint = PIP Digit = Ring PEM = mean	$j = 1$ (Technical)	
Joint = PIP Digit = Little PEM = mean	$j = 1$ (Technical)	
Joint = MCP Digit = Ring PEM = mean	$j = 2$ (Very minor)	
Joint = MCP Digit = Little PEM = mean	$j = 2$ (Very minor)	
Joint = PIP Digit = Ring PEM = mean	$j = 2$ (Very minor)	
Joint = PIP Digit = Little PEM = mean	$j = 2$ (Very minor)	

**Table xx:** Odds ratios for allocation for each level  $j = 1, \dots, 7$  from partial proportional odds model

Level	Odds ratio for allocation (95% CI)
$j = 1$ (Technical)	
$j = 2$ (Very minor)	
$j = 3$ (Mild)	
$j = 4$ (Moderate)	
$j = 5$ (Severe)	
$j = 6$ (Devastating)	
$j = 7$ (Death)	

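### SAP 8.4.11 takes every severity-specific risk difference for complications from a proportional odds model, which can attenuate or reverse the contrast for severe grades

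*SAP*

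**What the plan says.** Section 8.4.11 grades complications from 0 (none) to 7 (death) in Table 4. On the outcome to be modelled it says: "For further analyses, the highest ranked (i.e. worst) complication experienced will be used". The model is a mixed effect proportional odds model, "where the effect of each predictor is constrained to be the same for all levels of the outcome". From that fit the plan derives the between-arm difference in Pr(Y ≥ j) for j = 1 to 7, "and two-sided 95% CIs based on standard errors obtained via the delta method". The Appendix F template confirms the source: its title begins "Estimated absolute differences in proportions experiencing complication of level" and ends "from fitted proportional odds model".

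Three other outputs bear on the point:

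- **Crude description.** Numbers and proportions at each grade are reported by arm, and "The highest ranked complication experienced will be cross-tabulated with randomised group". No contrast or CI is attached.
- **Repeat without skin tears.** The same constrained model is refitted after removing skin tears at manipulation, which the plan regards as often an expected part of the procedure.
- **Partial proportional odds model.** The allocation effect is freed by level. The stated output is odds ratios only: "The estimated odds ratios for allocation for each outcome level will be reported together with 95% CIs". The Appendix F template lists levels 1 to 7. Table 4 describes the top level as "Death (unexpected in DISC and only allocated as a complication if it is directly attributable to the treatment or intervention".

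Section 8.4.11 does not say what to do with empty or sparse top grades, or which result leads if the two models disagree.

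**The concern.** Under proportional odds, one log odds ratio for allocation shifts every cut-point, so the modelled risk difference has the same sign at every grade. The data at the well-populated cut-points largely fix that ratio, and the result is then applied to the rare ones.

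Grade 2 is a retained stitch or a sore cast; grade 5 needs hospitalisation or re-operation. Injection with manipulation and open surgery could differ in one direction on the former and in the other on the latter. The plan allows for this possibility by adding a relaxed model and a repeat without skin tears.

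The severe grades would be read beside a non-inferiority conclusion on the PEM. If the only absolute difference with a CI at those grades follows the minor events, the account of serious harm could be muted or point the wrong way.

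**Working it through.** **Inputs from the SAP.** Section 3: margin 6, SD 22, one-sided 2.5%, 90% power, 284 per arm, 20% attrition. The SAP states no complication rates, so every rate below is an assumption.

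**Arm size.** The normal approximation is n = 2 × (1.960 + 1.282)² × 22² / 6² = 282.5, so 283 per arm. With the noncentral t, power is 89.95% at 283 and 90.05% at 284, which reproduces the plan's 284. Then 568 / 0.8 = 710, or 355 per arm. I use 355.

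**Method.** A two-arm proportional odds model (no covariates, no centre effect) was fitted by maximum likelihood to expected counts, with delta-method CIs for the risk differences. Sign errors come from 300 simulated trials per case.

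**Assumed grade distributions (%), grades 0 to 6, no deaths.** Surgery is 60, 5, 8, 12, 10, 3.5, 1.5 throughout: any grade 40%, grade 4 or worse 15%, grade 5 or worse 5%. Collagenase always has 2% at grade 5 or worse and varies below that:

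- A: 35, 5, 20, 25, 13, 1.5, 0.5
- B: 45, 5, 15, 20, 13, 1.5, 0.5
- C: 57, 5, 10, 14, 12, 1.5, 0.5
- D: 60, 5, 8, 12, 13, 1.5, 0.5
- E: 70, 4, 6, 9, 9, 1.5, 0.5

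**Results** (collagenase minus surgery, percentage points):

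| Case | Any grade, % | Common OR | Grade ≥4: true | Grade ≥4: model | Grade ≥5: true | Grade ≥5: model (95% CI) | Wrong sign at ≥5 | CI wholly on wrong side |
|---|---|---|---|---|---|---|---|---|
| A | 65 v 40 | 2.13 | 0.0 | +9.2 | -3.0 | +2.4 (+1.2 to +3.7) | 100% | 100% |
| B | 55 v 40 | 1.58 | 0.0 | +5.8 | -3.0 | +1.5 (+0.5 to +2.6) | 100% | 89% |
| C | 43 v 40 | 1.07 | -1.0 | +0.9 | -3.0 | +0.2 (-0.7 to +1.2) | 66% | 5% |
| D | 40 v 40 | 0.98 | 0.0 | -0.2 | -3.0 | -0.1 (-1.0 to +0.9) | 45% | 2% |
| E | 30 v 40 | 0.65 | -4.0 | -4.9 | -3.0 | -1.5 (-2.6 to -0.3) | 1% | 0% |

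**Direct contrast at grade 5 or worse.** SE = √(0.02 × 0.98/355 + 0.05 × 0.95/355) = 0.0137, so the difference is -3.0 points (Wald 95% CI -5.7 to -0.3). This is the same in all five cases, because it does not depend on the lower grades.

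**Reading.** Opposed effects (A, B) reverse the sign. With little or no difference in overall incidence (C, D), the severe contrast is almost erased. With both effects in the same direction (E), the sign is right and the difference at grade 5 or worse is about half its true size.

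**Empty top levels in the partial model.** If each arm has risk p of reaching a level, the chance that at least one arm has no event is 1 - (1 - q)², with q = (1 - p)^n:

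| p | n = 355 | n = 284 |
|---|---|---|
| 0.1% | 91% | 94% |
| 0.25% | 65% | 74% |
| 0.5% | 31% | 42% |
| 1% | 6% | 11% |

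With no event in one arm, the level's odds ratio is zero or infinite. With none in either arm, it does not exist.

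**The case against.** The strongest reply is that the plan has anticipated non-proportionality. It removes the one event type it singles out, frees the allocation effect by level, and tabulates crude proportions by grade. Section 8.6 adds counts of serious adverse events by allocation, and the adverse event tables list them individually. An opposed effect at grade 4 or 5 should appear as a level-specific odds ratio below 1 with its CI. Complications are a secondary outcome with no non-inferiority rule attached. Most of this stands, and a reader could detect a conflict. What remains is that none of these outputs is a severity-specific risk difference with a CI free of the constraint. Section 8.6 gives a risk difference only for any treatment-related event, whatever its severity. The repeat without skin tears uses the same constrained model, and case C shows what a small residual excess can do.

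Three stronger readings are tempting and are not supported:

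- **That minor events will drive the common odds ratio and the trial will report the wrong direction for serious harm.** The SAP gives no rates and no expected direction by grade, and Table 4 assigns no grade to skin tears. Reversal needs opposed effects.
- **That severe complications are reported only through this model.** The crude tables and the partial model show otherwise. The word only applies to absolute differences with CIs.
- **That the plan has an outcome-collapsing rule elsewhere and omitted it here.** The perfect-prediction rules in 8.4.7 and 8.4.12 pool reference digit, a covariate, or drop a model term. They do not merge outcome grades.

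**Conclusion.** The point holds as a limited gap that should be closed. Every severity-specific absolute difference with a CI rests on a constraint that the plan itself sees reason to relax, and the relaxed model is not asked for the same quantity. The size in this trial cannot be stated. In the assumed cases, a true -3.0 points at grade 5 or worse is reported as anything from -1.5 to +2.4. Those figures rest on assumed grade distributions, 355 per arm, and a model without covariates or centre effect. The same-sign property itself needs no assumption about rates.

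The sparse-level point is secondary. With no attributable deaths, which is what the plan expects, the level 7 odds ratio cannot be estimated. For grade 6 or worse, an empty arm is likely only if the risk is below about 0.5%.

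**What to change.** In section 8.4.11 and Appendix F:

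1. Beside the model, report the observed between-group risk difference with a score 95% CI (Newcombe or Miettinen-Nurminen) for grade 4 or worse and for grade 5 or worse, with and without skin tears. Section 8.4.12 already reports an unadjusted risk difference beside its model for further treatment. Alternatively, or in addition, derive the absolute differences from the partial proportional odds model already planned, which keeps the covariates.
2. State that the common odds ratio is an overall summary and that conclusions about severe grades rest on the unconstrained differences.
3. State that sparse top grades are merged in the partial model, for example 5 to 7, and change the template rows to match.

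The cost is a few lines of text and one extra table. The observed differences are unadjusted, and their CIs are wider than the model-based ones when events are rare.

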#### **8.4.12 Further treatment**

At each of the 3, 6, 12 and 24 month post treatment follow up visits, data pertaining to further treatments of the reference digit since the last visit are collected. If participants undergo further collagenase injection, limited fasciectomy surgery, dermofasciectomy or percutaneous needle fasciotomy to the reference digit at any point during follow up, then this will be counted as further treatment. Ongoing hand therapy and/or physiotherapy appointments to treat chronic regional pain syndrome, stiffness, swelling or scar problems, will also be considered further treatment. Participants who undergo more than six outpatient follow up visits for hand therapy and/or physiotherapy will have the details of these appointments reviewed on an individual basis to determine whether this extended duration of therapy should be considered to be further treatment or routine care.

The number of participants receiving further treatment to the reference digit will be reported by allocation, and the unadjusted odds ratio and risk difference will be reported (together with two-sided 95% CIs). The proportion of participants undergoing further treatment to the reference digit will be modelled using a mixed effects logistic regression model. This model will include allocation, study reference joint type (MCP or PIP), study reference digit and baseline PEM score as fixed effects with clustering by centre modelled using a random intercept. If perfect prediction occurs due to empty strata for some covariate combinations, then participants with study reference digit indicated as middle, index or thumb will be pooled so that reference digit becomes a three category covariate. If the issue persists, then the term for study reference joint will be dropped from the model. If baseline PEM score is missing then it will be imputed using predicted values via regression on baseline MHQ score. If MHQ score is also missing then baseline URAM score will be used. If baseline URAM score is also missing then mean imputation will be used. This model will be used to derive adjusted odds ratios and risk differences for allocation (together with two-sided 95% CIs).

We will also explore differences between the two groups in time elapsed between initial treatment and undergoing a further procedure to the reference digit. The proportion of participants yet to undergo a further procedure to the reference digit against time since treatment will be summarised with a Kaplan-Maier curve stratified by treatment group. Time from treatment to the first further procedure to the reference digit will be analysed using Cox proportional hazards regression adjusting for treatment group, study reference joint type (MCP or PIP), study reference digit and PEM score at baseline. A shared frailty for centre will also be included. Participants who reach the final follow up without having had a further procedure to the reference digit will be considered censored on the date of the final follow up. Any participant who withdraws from hospital follow up without having had a further procedure will be considered censored at the time of withdrawal. The proportional hazards assumption will be

evaluated through inspection of Kaplan-Meier curves and log-log plots and tested using Schoenfeld residuals [11, 12]. The hazard ratio for allocation (and two-sided Wald 95% CI) from the fitted model will be reported.

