#### **4. Randomisation**

The randomisation sequence was designed by the study statistician and is accessed via telephone or the internet using a secure, central randomisation service hosted by Sealed Envelope Ltd. This will ensure adequate allocation concealment for the study. This service will record information to identify all potential participants and their eligibility to avoid inappropriate entry of patients into the trial. The research team at each study site will access the system to complete randomisation following participant consent and completion of baseline assessments. Access to the system for representatives at individual sites will be coordinated and controlled by the trial project team at YTU. Both participants and clinicians will not be blind to allocation. The randomisation system has been designed to allocate participants 1:1 to each of the two study treatment arms. The system uses block randomisation with randomly varying block sizes, stratified by reference joint (MCP or PIP). The actual allocation sequence has been generated using a randomly generated seed provided by a statistician not involved in the ongoing or final analysis of the study.

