#### **8.4.7 Recurrence**

Recurrence will be defined in a binary manner (recurred or not recurred) at 6, 12 and 24 months post-treatment. Recurrence at the 6 month follow up is defined as an increase in passive extension deficit of the reference joint of 6° since the 3 month post treatment follow up. Recurrence at 12 and 24 months is defined as an increase in passive extension deficit of the reference joint of 20° since the 3 month post treatment follow up. These binary outcomes will be modelled using mixed effect logistic regression models adjusting for study reference joint (MCP or PIP), study reference digit, baseline PEM score and baseline passive extension measurement as fixed effects with centre as a random effect. These models will include all participants for whom the relevant (i.e. month 6 or month 12) binary indicator of recurrence can be derived using the available data. If perfect prediction occurs due to empty strata at some covariate combinations, then participants with study reference digit indicated as middle, index or thumb will be pooled so that reference digit becomes a three category covariate (little, ring, other). If the issue persists, then the term for study reference digit will be dropped from the model. If the baseline PEM score and/or baseline passive extension measurement is missing, then they will be imputed using predicted values via regression of the observed values on observed baseline MHQ scores and reference joint (MCP or PIP). If the MHQ score is also missing, then missing baseline PEM scores and/or baseline passive extension measurements will be imputed using predicted values via regression of the observed values on the observed baseline URAM scores and reference joint. If baseline URAM score is also missing then missing baseline PEM scores and/or baseline passive extension measurements will be imputed with the reference joint strata specific means. For both analyses, the estimated odds ratios for allocation (and two-sided 95% CIs) will be reported. This model will also be used to derive the absolute differences in risk of recurrence (together with two-sided 95% CIs) at representative values of the covariates (mean of the continuous covariates, both levels of reference joint, two levels of reference digit (ring or little) and marginalising over the centre random effects). We will also test composite null hypotheses about the absolute difference in incidence of recurrence at 12

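### The perfect-prediction fallback for further treatment drops reference joint, the stratification factor, where the parallel recurrence rule drops reference digit

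*SAP*

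**What the plan says.** Section 8.4.12 (Further treatment) specifies a logistic model with a random intercept for centre and these fixed effects: "This model will include allocation, study reference joint type (MCP or PIP), study reference digit and baseline PEM score as fixed effects". The fallback then has two steps.

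- Trigger: "If perfect prediction occurs due to empty strata for some covariate combinations".
- Step 1: "participants with study reference digit indicated as middle, index or thumb will be pooled so that reference digit becomes a three category covariate".
- Step 2: "If the issue persists, then the term for study reference joint will be dropped from the model".

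Section 8.4.7 (Recurrence) has a rule of the same shape.

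- Trigger: "If perfect prediction occurs due to empty strata at some covariate combinations".
- Step 1: the same three digits are "pooled so that reference digit becomes a three category covariate (little, ring, other").
- Step 2: "If the issue persists, then the term for study reference digit will be dropped from the model".

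Section 4 says that the allocation is "stratified by reference joint (MCP or PIP") and names no other stratification factor. Neither outcome section says why its second step differs from the other's.

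**The concern.** In both sections the first step acts on digit, so the rule presumes that a thinly populated digit category is the cause of the perfect prediction. If pooling does not cure it, the natural next step is to remove digit, as Section 8.4.7 does. Section 8.4.12 removes joint and leaves the pooled digit term in the model.

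Two things follow if the sentence is applied as written. The adjusted further-treatment estimates lose the factor by which the trial was randomised. And if no one in the pooled digit category has further treatment, that category still predicts the outcome perfectly, so its coefficient still has no finite maximum likelihood estimate. The rule ends there, and the analyst would have to choose the next step after seeing the data.

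**Working it through.** **Comparison of the text.** Trigger and first step agree in Sections 8.4.7 and 8.4.12; only the term dropped at the end differs. Joint is described as the stratification factor and kept at each fallback step for PEM (Sections 8.2.3 and 8.2.4), URAM (8.4.3), MHQ (8.4.4) and SANE (8.4.5). It is also kept by the recurrence fallback. Section 8.4.12 is the only place where the SAP drops it.

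**Size of the trial used in the check.** The point rests on no figure in the SAP, but the check takes its sample size from Section 3, so that was reproduced first. With margin 6, SD 22, one-sided 2.5% and 90% power:

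n per arm = 2 × (1.960 + 1.282)² × 22² / 6² = 282.5, so 283 by the normal approximation.

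The exact t-test calculation gives power 0.8995 at 283 and 0.9005 at 284 per arm. That confirms 284 per arm and 568 in total, and 568 / 0.80 = 710.

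**Does either step cure the problem?** Trials of N = 568 were simulated with the main effects of Section 8.4.12: allocation, joint, three-category digit and baseline PEM. The centre random intercept was left out. The event rate (3%, 5%, 10%), the share of participants in the pooled digits (5%, 10%, 15%) and a 50% PIP share are assumptions, because the SAP gives none of them. Events were generated independently of the covariates, with 300 data sets per scenario. Each was tested for complete or quasi-complete separation by linear programming, then tested again with joint removed and with digit removed.

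As a cross-check, the probability that the pooled category contains no event is (1 − event rate × share)^568. For 3% and 5% this is (1 − 0.0015)^568 = 0.426.

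| Event rate | Pooled-digit share | Probability of no event in pooled digits | Separated after pooling | Cured by dropping joint | Cured by dropping digit |
|---|---|---|---|---|---|
| 3% | 5% | 0.426 | 134 of 300 | 0 | 134 |
| 3% | 10% | 0.181 | 51 of 300 | 0 | 51 |
| 3% | 15% | 0.077 | 17 of 300 | 0 | 17 |
| 5% | 5% | 0.241 | 72 of 300 | 0 | 72 |
| 5% | 10% | 0.058 | 14 of 300 | 0 | 14 |
| 5% | 15% | 0.014 | 3 of 300 | 0 | 3 |
| 10% | 5% | 0.058 | 14 of 300 | 0 | 14 |
| 10% | 10% | 0.003 | 0 of 300 | – | – |
| 10% | 15% | 0.0002 | 0 of 300 | – | – |

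The separated data sets add up to 134 + 51 + 17 + 72 + 14 + 3 + 14 = 305. Dropping joint cured 0 of 305 and dropping digit cured 305 of 305. The simulated frequencies lie close to the closed-form probabilities, as expected if an eventless pooled category is the source.

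A constructed data set of 568 with no event in the pooled category gives the same answer: separated as it stands, still separated without joint, not separated without digit.

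**The case against.** The strongest case against is that this matters little and may never arise. The unadjusted odds ratio and risk difference are reported whatever happens to the adjusted model. Section 8.4.12 also has a Cox model for time to a further procedure that adjusts for joint, with no rule that drops it. The primary outcome and the non-inferiority conclusion are untouched. All of this stands, and it limits the size of the point.

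Three stronger readings are tempting, and the SAP does not support them.

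- A reader might infer that re-treatment is rare, so the rule will probably be needed. The SAP gives no event rate, and its definition counts some ongoing hand therapy and physiotherapy as well as repeat procedures, which could raise the rate considerably. At 10% events with 10% or more in the pooled digits, the trigger was never reached in the simulation.
- A reader might call the two sections contradictory. They govern different models for different outcomes, so both can be followed. This is an unexplained inconsistency between parallel rules, most likely a slip of digit for joint.
- A reader might say that joint can never be the source of separation. The SAP gives no MCP/PIP split and no events by joint. If one joint stratum had no events, dropping joint would help. That is unlikely for a two-level factor, and it happened in none of the simulated data sets under an assumed even split, but it is an assumption.

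None of these gives a reason for the present wording.

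**Conclusion.** The point holds as a correction of limited reach. As written, the last step of the Section 8.4.12 fallback removes the only stratification factor, leaves in place the term that the rule itself treats as the cause, and provides nothing further. It also departs without explanation from the otherwise matching rule in Section 8.4.7.

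What is exposed is the adjusted odds ratio and adjusted risk difference for one secondary outcome, and only if perfect prediction survives pooling. How often that would happen cannot be stated from the SAP; across the assumed scenarios it ranged from 134 of 300 to 0 of 300. The finding that dropping joint does not cure separation arising from a sparse digit category does not depend on those assumed rates: an eventless category remains eventless whether or not joint is in the model. The simulation ignores the centre random intercept and takes events as unrelated to the covariates.

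**What to change.** In the fallback sentence of Section 8.4.12, replace *study reference joint* with *study reference digit*. Allocation, joint, baseline PEM and the centre random intercept then stay in the model, and the rule matches Section 8.4.7. If dropping joint was intended, the SAP should say why the two sections differ.

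No Firth step is needed. Dropping digit removed the separation in every data set examined. The SAP uses Firth regression only for models of missingness and withdrawal, and substituting it here would lose the centre random intercept.

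The cost is one word in the SAP, before the analysis is run. No sample size, data collection or primary analysis changes.
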